3.1.2. Secondary Efficacy Endpoints

Secondary efficacy endpoints are provided below:

- Annualized flare rate by British Isles Lupus Assessment Group (BILAG)-2004 flare index through Day 169 all flares
- Time-to-first flare by BILAG-2004 flare index
- Achievement of Lupus Low Disease Activity State (LLDAS) at Day 169
- Change from baseline in Systemic Lupus Erythematosus Disease Activity Index 2000 (SLEDAI-2K) total score at Day 169
- Cumulative prednisone-equivalent dose use (total area under the curve of daily prednisone-equivalent dose) through Day 169
- Achievement of ≥50% reduction in Cutaneous Lupus Erythematosus Disease Area and Severity Index (CLASI) activity score at Day 169 in the subgroup of subjects with baseline CLASI activity score ≥8

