6.21. Restricted/Rescue Medications

During the Treatment Period, subjects treated with new concomitant medications or increased dose of the existing treatment will be considered non-responders (treatment failures) for assessments of SRI-X, BICLA, SLEDAI-2K Improvement, and 50% Improvement in CLASI activity score efficacy endpoints for visits after taking the restricted medication. Criteria for restricted/rescue medications include the following:

- Oral corticosteroids (prednisone, methylprednisolone, prednisolone, fludrocortisone acetate) can be taken during the study per the protocol criteria however the following would qualify the subject as a treatment failure:
 - Increase in dose from baseline of oral corticosteroids (burst) from Day 1 through Day 141 lasting more than 14 days (i.e., subject must taper back down to baseline dose level by Day 14 of the increase; for subjects not previously taking oral corticosteroids, taper must be down to 0 mg/day within 14 days); such a course also cannot be initiated more frequently than every 28 days
 - Dose greater than 40 mg prednisone/day (or equivalent)
 - Initiation of new oral corticosteroids or an increase in dose after Day 141
- Intramuscular corticosteroids can be taken during the study however, the following would qualify the subject as a treatment failure:
 - Intramuscular methylprednisolone dose greater than 160 mg administered at a single timepoint from Day 1 through Day 169
 - Intramuscular corticosteroids given at a frequency greater than 28 days
 - Initiation of new intramuscular corticosteroids or an increase in dose after Day 141

- Topical corticosteroids can be taken during the study however, the following would qualify the subject as a treatment failure
 - Increase in dose from baseline of topical corticosteroids (burst) from Day 1 through Day 141 lasting more than 14 days (i.e., subject must taper back down to baseline dose level by Day 14 of the increase; for subjects not previously taking topical corticosteroids, taper must be down to 0 mg/day within 14 days); such a course also cannot be initiated more frequently than every 28 days
 - Initiation of new topical corticosteroids or an increase in dose after Day 141
- Intravenous corticosteroids
- Increase in dose or addition of hydroxychloroquine or hydroxychloroquine-like drugs (hydroxychloroquine, hydroxychloroquine sulfate, chloroquine phosphate)

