7.8.1. Treatment-Emergent Adverse Events

AEs will be recorded at all scheduled and unscheduled visits during the study. Summaries will be presented for TEAEs. In this study, signs and symptoms of SLE activity are captured in the disease activity assessments and will not be reported as AEs. Clinically significant changes in physical exam findings, laboratory test results, and ECG results will be recorded and analyzed as AEs. The incidence, seriousness, and severity of TEAEs and the relationship of the events to study drug will be used to assess safety.

All AEs terms will be classified using MedDRA and reported based on system organ classes and preferred terms. Adverse event severity will be graded using Common Terminology Criteria for Adverse Events (CTCAE), version 5.0. AEIs will be reviewed by the medical monitor lead.

In general, the incidence of AEs will be summarized by the number and the percentage of unique subjects in the safety population who experiencing an event. As such, subjects who report the

same event on multiple occasions will only be counted once. A by-subject listing of all AEs reported will be provided. Rules for the imputation of missing and partial AE dates and missing designations of AE severity, relatedness and seriousness are defined in Section 13.

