Missing Safety Information:

For analyses of AE data, events with missing severity grade will be imputed as Grade 3 for analysis. Similarly, AEs with missing relationship to study drug will be imputed as drug-related. If no designation of event seriousness is available, the AE will be considered serious.

Missing and Partial Dates:

Algorithms applied for imputing partial and missing date values are described below:

Table 7: Imputation of Partial and Missing Date Values

Partial/Missing Start or Stop Date	Imputed Start Date	Imputed Stop Date
Missing year, month, and day	Date of randomization visit	
Missing month and day, and the year is present	Date of randomization visit if the year is the same as the year of randomization date, else January 1 of the start year.	December 31 of that year
Missing day, but year and month are present	Date of randomization visit if the year and month are the same as the year and month of randomization date, else the 1st of the start month.	Last day of that month
Missing month, but year and day are present	Assume day is also missing and impute as above	Missing month imputed as December

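### If SAP Table 7 is applied to steroid records, a permitted burst with a missing stop day can be scored as longer than 14 days, and so as treatment failure

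*SAP*

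**What the plan says.** SAP Section 13, Table 7 gives three rules for a partial stop date:

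- day missing: "Last day of that month"
- month and day missing: "December 31 of that year"
- month missing but day present: "Missing month imputed as December"

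The table is introduced in general terms: "Algorithms applied for imputing partial and missing date values are described below". It names no data type, makes no exception for medication records, and sets no cap at the next dose record, Day 169 or the last study date. The one pointer to these rules elsewhere in the SAP text is in 7.8.1 and concerns adverse events: "Rules for the imputation of missing and partial AE dates and missing designations of AE severity, relatedness and seriousness are defined in Section 13".

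SAP 6.21 lists among its treatment-failure criteria "Increase in dose from baseline of oral corticosteroids (burst) from Day 1 through Day 141 lasting more than 14 days". Topical steroids have a parallel 14-day test. Failure applies at later visits for SRI-X, BICLA, SLEDAI-2K improvement and 50% CLASI improvement. SAP 7.4.2 scores restricted or rescue medication as non-response for binary endpoints and excludes later SLEDAI-2K total scores from the MMRM. SAP Table 2 applies the same non-response rule to LLDAS. SAP 3.1.2 lists as a secondary endpoint "Cumulative prednisone-equivalent dose use (total area under the curve of daily prednisone-equivalent dose) through Day 169".

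On the protocol side, 4.4.4 says steroid doses are captured as concomitant medications. Section 8.2.2.3 allows an oral burst of up to 40 mg prednisone per day, provided the subject is back at the Day 1 dose by the end of the 14th day after initiation.

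**The concern.** A late stop date is an ordinary cautious choice when the question is how long an adverse event lasted. Here the same rule could feed a duration test that decides the primary efficacy endpoints. The test allows 14 days, and month-end imputation can add up to a month. A subject who stayed within the protocol's burst limits could therefore be scored as having used rescue, on the strength of an unrecorded day. The affected outputs would be SRI-4 and BICLA at Day 169, the 50% CLASI and LLDAS responses, the SLEDAI-2K MMRM and the prednisone AUC, which would include doses never taken.

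**Working it through.** **Plan's own figure.** The documents give none for date imputation. The nearest is the power statement in protocol 10.2 and SAP Table 1, used below only for scale. A two-sided chi-square test at 0.05 with 65 per arm gives 82.2% (40% vs 65%) and 86.9% (20% vs 45%), against the stated 82% and 87%. It reproduces.

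**Inputs and assumptions.** The stop-date rule is from SAP Table 7 and the 14-day limit from SAP 6.21. Assumed: start date known, only the stop day missing, start day uniform over the month, and length counted inclusively. Let s be the start day in a month of M days, L ≤ 14 the true length, and M′ the length of the next month.

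**Imputed length.**
- Burst ends in the same month: M − s + 1. This exceeds 14 only if s ≤ M − 14, which is day 17 or earlier when M = 31.
- Burst crosses into the next month: M + M′ − s + 1. This always exceeds 14.

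The start days that escape run from M − 13 to M − L + 1, which is 15 − L days. So the share wrongly above 14 days is 1 − (15 − L)/M.

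For M = 31 and M′ = 30:

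| True length L | Start days scored above 14 | Share |
|---|---|---|
| 5 | 21/31 | 68% |
| 7 | 23/31 | 74% |
| 10 | 26/31 | 84% |
| 14 | 30/31 | 97% |

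The mean imputed length is (475 + 201)/31 = 21.8 days for L = 7 and (405 + 481)/31 = 28.6 days for L = 14. At a constant 40 mg/day (illustration), a 7-day burst of 280 mg is counted on average as 21.8 × 40 = 872 mg.

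**Whole-year check.** Over 365 start dates the share is 1 − 12(15 − L)/365: 54% for L = 1, 74% for L = 7, 97% for L = 14, and 75% averaged over L = 1 to 14. The mean excess is 14.7 days. With month and day both missing it is 1 − (15 − L)/365, or 96% to 99.7%.

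**Reading of the limit.** If the limit is taken as 15 inclusive days, the 31-day-month shares are 22/31 = 71% (L = 7) and 29/31 = 94% (L = 14).

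**Examples at 40 mg/day, stop day missing.**

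| True burst | True days, mg | Imputed days, mg | Scored as failure? |
|---|---|---|---|
| 3–9 March | 7, 280 | 29, 1,160 | Yes, wrongly |
| 28 March–6 April | 10, 400 | 34, 1,360 | Yes, wrongly |
| 20–26 March | 7, 280 | 12, 480 | No, but dose inflated |
| 18–31 March | 14, 560 | 14, 560 | No change |

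A year-only stop on a burst starting on Day 30 could run to Day 169, where the AUC ends: 169 − 30 + 1 = 140 days, or 5,600 mg.

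**Size per subject.** SAP 4.1 says enrollment stopped at 76, or about 38 per arm if split evenly. One responder wrongly failed moves an arm by 1/38 = 2.6 points (1/65 = 1.5 at the planned size). For scale, under the 25-point scenarios one such loss in the ALPN-101 arm alone takes power at 38 per arm from 59% to 50% (SRI-4) and from 65% to 56% (BICLA). A loss in the placebo arm alone would widen the observed difference instead.

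**The case against.** The strongest reply concerns scope. Nothing in the SAP says that Table 7 covers medication dates or that imputed dates feed the 14-day test or the AUC. The only pointer names adverse events, and the table follows the rules for missing safety information. SAP 6.12, 6.13, 6.16, 6.19, 6.20 and 7.5.2 are not in the public text, and no definition of cumulative prednisone is visible, so a steroid-specific rule may exist there. This stands as a limit on certainty. It does not remove the point, because partial dates have their own heading in Section 13, which is not confined to safety, and no other date rule is visible. If Table 7 is for adverse events only, the visible plan has no rule for dates that decide primary-endpoint failure.

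Second, SAP 6.21 ends a burst at return to the baseline dose, so for a subject on baseline steroids the dated start of the resumed dose may settle its length. That is right where such a record exists.

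Third, bursts are well observed. The protocol asks for assessments before a burst, and Table 1 records concomitant medications at every two-weekly dosing visit. Missing stop days may be few, and year-only dates rarer still. The documents neither confirm nor exclude this.

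Fourth, late imputation is conservative for response and fits the non-responder approach. That is true within an arm, but it does not make the comparison between arms conservative.

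A reader might also infer that a baseline record stretched to month-end would overlap a burst record and push the daily dose above 40 mg. That requires overlapping records to be summed, which the visible text does not specify, so the point does not rest on it.

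**Conclusion.** The point holds conditionally. If Table 7 is applied to steroid records, a permitted burst with a missing stop day can be scored as lasting more than 14 days, for about 74% of start days at 7 days' true length and 97% at 14. These shares are conditional on the stop day being missing. They are not the share of all bursts affected.

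Three stronger readings are not supported:

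- That every such burst becomes a failure. A burst that starts after day 17 of a 31-day month and ends in that month does not.
- That every misclassified subject shifts the result. On the response endpoints a false failure matters only if the subject would otherwise have responded, and AUC inflation stops at Day 169.
- That the bias has a known direction. It might fall on the arm with more bursts, but the documents give neither burst rates by arm nor the number of partial stop dates.

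At about 38 per arm, each responder wrongly failed costs that arm 2.6 points, so a few records could matter. The SAP should be clarified before lock.

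**What to change.** State in Table 7 how it applies to corticosteroid and other SLE medication records used in SAP 6.21, 7.2 and 3.1.2. For those records:

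1. Set a partial stop date to the earliest of: the day before the next dose record of the same drug; the day before the first later visit at which the drug is recorded as no longer ongoing; the end of the known month or year; and the last study date. Never set it before the record's start date.
2. Do not let records for the same course overlap.
3. Do not let an imputed stop date alone trigger treatment failure. Query the site before lock, and if the date stays unresolved, classify the burst by blinded review.
4. Add a sensitivity analysis of SRI-4, BICLA and prednisone AUC using the earliest and latest possible stop dates.

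Using the day before the visit matters. A burst from Day 57 closed at the Day 71 visit counts as 71 − 57 + 1 = 15 days, but closed on Day 70 it counts as 14. Step 1 is not sufficient by itself: with windows of ±3 days at both visits, the gap can reach 14 + 3 + 3 = 20 days. Step 3 is therefore needed.

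The cost is SAP wording, a few lines of programming and probably a small number of queries. The downside is that a burst that truly overran but has an incomplete date could be scored as compliant. The query and the sensitivity analysis limit that risk.

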15. APPENDICES

15.1. Study Overview

Figure 1: Study Overview

Notes: ADA=Anti-drug antibodies; CLASI=Cutaneous Lupus Erythematosus Disease Area and Severity Index; BILAG=British Isles Lupus Assessment Group; PGA= Physician's Global Assessment; PROs=Patient - Reported Outcomes; PK=Pharmacokinetics; SLE=Systemic lupus erythematosus; SLEDAI=SLE Disease Activity Index.

15.2. Schedule of Assessments

Table 8: Schedule of Procedures and Assessments

Study Period:								Treatm	nent1								ЕоТ	EoS ²
Visit:	Screen	1	$1b^3$	$1c^3$	$1d^3$	2	3	4	5	6	7	8	9	10	11	12	13	
Day:	-42 to -1	1	2	4	8	15	29	43	57	71	85	99	113	127	141	155	169	197
Visit Window:	NA	NA	NA	± 1	± 1	± 1	± 2	± 2	± 3	± 3	± 3	± 3	± 3	± 3	± 3	± 3	± 3	± 3
Demographics	X																	
Medical History	X	X ⁵																
Eligibility Review	X ⁴	X ⁵																
Chest X-ray	$\chi^{^6}$																	
Physical Exam ⁷	X	X^{5}				X^8	X^8	X^{8}	X^8	X^8	X^8	X^8	X^{8}	X^8	X^{8}	X ⁸	X^{8}	X
Electrocardiogram	X	2X9									2X9					2X9		X
Weight	X	X^{5}					X		X		X		X		X		X	X
Vital Signs	X	2X9				2X9	2X9	2X9	2X9	2X9	2X9	2X9	2X9	2X9	2X9	2X9	X	X
SLE Damage Assessment (SDI)		X^{5}															X	X
Physician SLE Assessment ¹⁰	X ¹¹	X^{5}				X ¹²	X		X		X		X		X		X	X
Skin Photography ¹³	X	X				X	X		X		X		X		X		X	X
Patient SLE Assessment ¹⁴		X 5					X		X		X		X		X		X	X
Safety Lab Evaluations ¹⁵	X ¹⁶	X^{5}				X	X		X		X		X		X		X	X
Infectious Disease Screen ¹⁷	X																	
Urine Pregnancy Test ¹⁸	X	X^{5}				X	X	X	X	X	X	X	X	X	X	X	X	X
Clinical Biomarkers of SLE ¹⁹	X	X 5				X	X		X		X		X		X		X	X
PK/ADA		2X9				X	X		X		2X9		X		X	2X9	X	X
(Dense PK Subject Subset) ²¹		$(3X^{22})$	(X)	(X)	(X)	(X)	(X)		(X)		(2X ⁹)		(X)		(X)	(2X ⁹)	(X)	(X)
(DNA) ²¹		X																
Randomization		X																
Study Drug Administration ²³		X				X	X	X	X	X	X	X	X	X	X	X		
Concomitant Medications		X	(X)	(X)	(X)	X	X	X	X	X	X	X	X	X	X	X	X	X
Adverse Events ²⁴		X	(X)	(X)	(X)	X	X	X	X	X	X	X	X	X	X	X	X	X

- 1 On the days of study drug administration, all assessments and procedures must be performed prior to dosing except where otherwise specified.
- 2 Assessments should also be performed in the event of early discontinuation.
- 3 Visit held only for subjects in the Dense PK/ ubset.
- 4 Investigator's screening eligibility assessment must be reviewed and confirmed by Sponsor or designee.
- 5 Perform prior to randomization and study-drug dosing.
- 6 This requirement may be met with documentation of a previous chest x-ray performed within 3 months of Screening.
- 7 Complete physical examination required at Screening, Baseline, and EoS or early discontinuation.
- A problem-oriented exam may be performed at the physician's discretion; however, at applicable visits, physical examination required for SLEDAI and BILAG assessment must be performed.
- Obtain pre-dose, and then at 10 minutes (\pm 10 min) following completion of infusion.
- 10 BILAG, SLEDAI-2K 30 (or SLEDAI-2K on Day 15 per footnote 12), PhGA, CLASI, will be conducted at Screening (see footnote 11) and Day 15 (see footnote 12).
- 11 SLEDAI-2K 30, BILAG, and PhGA; lupus history should be recorded at Screening.
- 12 SLEDAI-2K, PhGA.
- 13 Skin photography should be performed as indicated if any abnormalities are recorded on CLASI.
- 14 PtGA, SF-36, FACIT-F (13-item). Note: Patient's assessments should be completed before physician's assessment.
- 15 Collect blood and urine samples using kit provided by the central laboratory.
- 16 In addition to standard safety lab evaluations, includes TSH.
- 17 Collect samples using kit provided by the central laboratory.
- 18 Perform at the clinical site using provided kit; negative results must be confirmed prior to study drug dosing.
- 19 Collect blood samples using kit provided by the central laboratory.
- 20 Pharmacokinetics, anti-drug antibodies, detailed timepoints and instructions.
- 21 In subjects who provide supplemental consent.
- Obtain pre-dose, and then at 10 minutes (\pm 10 min) and 4 hours (\pm 30 min) following completion of infusion.
- 23 Subjects should be observed for at least 2 hours following their first infusion of study drug and for 30 minutes following each subsequent infusion.
- 24 For oral mucocutaneous lesions reported as AEIs, photographic documentation should be collected at presentation and in the event of significant change (as detailed in the Procedures Manual).

Abbreviations: ADA, Anti-drug antibodies; AEI, Adverse event of interest: BILAG, British Isles Lupus Assessment Group index; CLASI, Cutaneous Lupus Erythematosus Disease Area and Severity Index; EoS, End of study; EoT, End of treatment; FACIT-F, Functional Assessment of Chronic Illness Therapy-Fatigue; PhGA, Physician's Global Assessment of SLE Disease Activity; PK, Pharmacokinetics; PtGA, Patient's Global Assessment of Disease Activity; SDI, Systemic Lupus International Collaborating Clinics/American College of Rheumatology (SLICC/ACR) Damage Index; SF-36, Short Form-36; SLE, Systemic lupus erythematosus; SLEDAI, Systemic Lupus Erythematosus Disease Activity Index; TSH, Thyroid stimulating hormone.

15.3. Disease Assessment Tools

15.3.1. **SLEDAI-2K**

The SLEDAI-2K is a global measure of disease activity. The raw data set contains responses for 24 items, each of which are assigned weighted scores of 1 to 8 points. The total score is the sum of the weights of the items which are present at the time of assessment. The range of the SLEDAI total score is 0 to 105.

Weighted SLEDAI-2K scores for the presence of each of the 24 items on the data collection tool are shown in below.

Table 9: SLEDAI Weighted Score by Item

Organ System	Item Name	Description	Score
Neuropsychiatric	Seizure	Recent onset, exclude metabolic, infectious or drug causes	8
	Psychosis	Altered ability to function in normal activity due to severe disturbance in perception of reality. Include hallucinations, incoherence, marked loose associations, impoverished thought content, marked illogical thinking, bizarre, disorganized, or catatonic behavior. Exclude uraemia and drug causes	8
	Organic Brain Syndrome	Altered mental function with impaired orientation, memory, or other intellectual function, with rapid onset and fluctuating clinical features, inability to sustain attention to environment, plus at least 2 of the following: perceptual disturbance, incoherent speech, insomnia or daytime drowsiness, or increased or decreased psychomotor activity. Exclude metabolic, infectious or drug causes	8
	Cranial Nerve Disorder	New onset of sensory or motor neuropathy involving cranial nerves	8
	Lupus Headache	Severe, persistent headache; may be migrainous, but must be non-responsive to narcotic analgesia	8
	CVA	New onset cerebrovascular accident(s). Exclude arteriosclerosis.	8
Ophthalmic	Visual Disturbance	Retinal changes of SLE. Include cytoid bodies, retinal hemorrhages, serous exudates or hemorrhages in the choroid, or optic neuritis. Exclude hypertension, infection, or drug causes	8
Mucocutaneous	Vasculitis	Ulceration, gangrene, tender finger nodules, periungual infarction, splinter hemorrhages or biopsy or angiogram proof of vasculitis	8
	Rash	Inflammatory type rash	2
	Alopecia	Abnormal, patchy or diffuse loss of hair	2
	Mucosal ulcers	Oral or nasal ulcerations	2

Organ System	Item Name	Description	Score
Musculoskeletal	Arthritis	≥2 joints with pain and signs of inflammation	4
	Myositis	Proximal muscle aching/weakness, associated with elevated creatinine phosphokinase/aldolase, or EMG changes or a biopsy showing myositis	4
Renal	Urinary Casts	Heme-granular or RBC casts	4
	Hematuria	>5 RBC/high power field. Exclude stone, infection or other cause	4
	Proteinuria	>0.5 gram/24 hours	4
	Pyuria	>5 WBC/high power field. Exclude infection	4
Cardiorespiratory	Pleurisy	Pleuritic chest pain or pleural rub with effusion, or pleural thickening (requires objective component)	2
	Pericarditis	Classic pericardial pain and/or rub, effusion with ECG or echocardiogram confirmation	2
Hematological	Low complement	Decrease in CH50, C3 or C4 below lower limit of normal for testing laboratory	2
	Increased DNA Binding	Increased DNA binding above normal range for testing lab	2
	Thrombocytopenia	<100 x 10 ⁹ platelets/L, exclude drug causes	1
	Leukopenia	<3 x 10 ⁹ WBC/L, exclude drug causes	1
Constitutional	Fever	>38°C Exclude infectious cause	1

Source: Gladman, 2000.

Notes: C3=Complement component 3; C4=Complement component 4; CH50=Total complement; CVA=Cerebrovascular accident; ECG=Electrocardiogram; EMG=Electromyogram; RBC=Red blood cell;

SLE=Systemic lupus erythematosus; WBC=White blood cell.

15.3.2. BILAG 2004

The BILAG 2004 index is an 86-item assessment of nine organ domains. The first seven organ systems (constitutional, mucocutaneous, neuropsychiatric, musculoskeletal, cardiorespiratory, gastrointestinal, and ophthalmic) contain clinical parameters which are assessed by the investigator and given scores of 0=not present, 1=improving, 2=same, 3=worse, or 4=new. Renal and haematologic scores are based on laboratory values reported at the time of assessment. The numeric parameter scores within each organ system are used to assign a letter grade indicating disease activity. Table 10 displays each level of organ system grading.

Table 10: BILAG Organ System Grades

BILAG Grade	Description
BILAG A	Requires disease-modifying treatment such as prednisone >20 mg/day or immunosuppressant
BILAG B	Mild, reversible problems requiring symptomatic therapy such as anti-malarials, NSAIDS, or prednisone ≤20 mg/day
BILAG C	Stable, mild disease
BILAG D	System previously involved but not currently active
BILAG E	System never involved

Notes: BILAG=British Isles lupus assessment group; NSAIDS=Non-steroidal anti-inflammatory drugs

Table 11 lists the grading algorithms for each body system.

Table 11: BILAG Grading Algorithms

	BILAG Grade										
Organ System	A	В	С	D	E						
Constitutional	Pyrexia recorded as 2 (same), 3 (worse) or 4 (new) AND Any 2 or more of the following recorded as 2 (same), 3 (worse) or 4 (new): Weight loss Lymphadenopathy/ splenomegaly Anorexia	Pyrexia recorded as 2 (same), 3 (worse) or 4 (new) OR Any 2 or more of the following recorded as 2 (same), 3 (worse) or 4 (new): • Weight loss • Lymphadenopathy/ splenomegaly • Anorexia BUT do not fulfill criteria for Category A	Pyrexia recorded as 1 (improving) OR One or more of the following recorded as >0: • Weight loss • Lymphadenopathy/ splenomegaly • Anorexia BUT does not fulfill criteria for category A or B	Previous involvement, currently inactive	No previous involvement						
Mucocutaneous	Any of the following recorded as 2 (Same), 3 (Worse), or 4 (New): Skin eruption – severe Angio-oedema – severe Mucosal ulceration – severe Panniculitis/ Bullous lupus – severe Major cutaneous vasculitis/thrombosis	Any Category A features recorded as 1(Improving) OR Any of the following recorded as 2 (Same), 3 (Worse) or 4 (New): Skin eruption – mild Panniculitis/Bullous lupus – mild Digital infarcts or nodular vasculitis Alopecia-severe	Any Category B features recorded as 1(Improving) OR Any of the following recorded as 1(Improving), 2 (Same), 3 (Worse) or 4 (New): • Angio-oedema – mild • Mucosal ulceration – mild • Alopecia – mild • Periungual erythema/chilblains • Splinter haemorrhages	Previous involvement, currently inactive	No previous involvement						

	BILAG Grade										
Organ System	A	В	С	D	E						
Neuropsychiatric	Any of the following recorded as 2 (Same), 3 (Worse) or 4 (New):	Any Category A features recorded as 1 (Improving) OR Any of the following recorded as 2 (Same), 3 (Worse) or 4 (New): • Seizure disorder • Cerebrovascular disease (not due to vasculitis) • Cognitive dysfunction • Movement disorder • Autonomic disorder • Headache severe unremitting • Headache due to raised intracranial hypertension	Any Category B features recorded as 1 (improving)	Previous involvement, currently inactive	No previous involvement						
Musculoskeletal	Any of the following recorded as 2 (Same), 3 (Worse) or 4 (New): • Myositis-severe • Arthritis (severe)	Any Category A features recorded as 1 (Improving) OR Any of the following recorded as 2 (Same), 3 (Worse) or 4 (New): • Myositis-mild • Arthritis (moderate)/ Tendonitis/Tenosynovitis	Any Category B features recorded as 1 (Improving) OR The following recorded as 1 (Improving), 2 (Same), 3 (Worse) or 4 (New): • Arthritis (mild)/ Arthralgia/ Myalgia	Previous involvement, currently inactive	No previous involvement						

	BILAG Grade				
Organ System	A	В	С	D	E
Cardiorespiratory	Any of the following recorded as 2 (Same), 3 (Worse) or 4 (New): Myocarditis/Endocarditis + Cardiac failure Arrhythmia New valvular dysfunction Cardiac tamponade Pleural effusion with dyspnoea Pulmonary haemorrhage/vasculitis Interstitial alveolitis/ pneumonitis Shrinking lung syndrome Aortitis Coronary vasculitis	Any Category A features recorded as 1 (Improving) OR Any of the following recorded as 2 (Same), 3 (Worse) or 4 (New): • Pleurisy/Pericarditis • Myocarditis – mild	Any Category B features recorded as 1 (improving)	Previous involvement, currently inactive	No previous involvement
Gastrointestinal	Any of the following recorded as 2 (Same), 3 (Worse) or 4 (New): Peritonitis Lupus enteritis/colitis Intestinal pseudo-obstruction Acute lupus cholecystitis Acute lupus pancreatitis	Any Category A feature recorded as 1 (Improving) OR Any of the following recorded as 2 (Same), 3 (Worse) or 4 (New): • Abdominal serositis or ascites • Malabsorption • Protein-losing enteropathy • Lupus hepatitis	Any Category B features recorded as 1 (improving)	Previous involvement, currently inactive	No previous involvement

BILAG Grade					
Organ System	A	В	С	D	E
Ophthalmic	Any of the following recorded as 2 (Same), 3 (Worse) or 4 (New): Orbital inflammation/myositis/proptosis Keratitis – severe Posterior uveitis/retinal vasculitis – severe Scleritis – severe Retinal/choroidal vaso- occlusive disease Optic neuritis Anterior ischaemic optic neuropathy	Any Category A features recorded as 1 (Improving) OR Any of the following recorded as 2 (Same), 3 (Worse) or 4 (New): • Keratitis – mild • Anterior uveitis • Posterior uveitis/retinal vasculitis – mild • Scleritis-mild	Any Category B features recorded as 1 (Improving) OR Any of the following recorded as 1 (Improving), 2 (Same), 3 (Worse) or 4 (New): • Episcleritis • Isolated cotton-wool spots (cytoid bodies)	Previous involvement, currently inactive	No previous involvement
Renal	Two or more of the following providing 1, 4 or 5 is included: 1. Deteriorating proteinuria (severe): a. urine dipstick increased by ≥2 levels (only if other methods of urine protein estimation not available); or b. 24-hour urine protein >1 g that has not decreased by ≥25%; or c. urine protein-creatinine ratio >100 mg/mmol that has not decreased by ≥25%; or d.urine albumin-creatinine ratio >100 mg/mmol that has not decreased by ≥25% 2. Accelerated hypertension 3. Deteriorating renal function (severe): a. plasma creatinine >130 μmol/L and having risen to >130% of previous value; or b. GFR having fallen to <67% of previous value; or	One of the following: 1. One of the Category A features 2. Proteinuria (not fulfilling Category A criteria): a. urine dipstick which has risen by 1 level to at least 2+ (only if other methods of urine protein estimation not available); or b. 24-hour urine protein ≥0.5 g that has not decreased by ≥25%; or c. urine protein-creatinine ratio ≥50 mg/mmol that has not decreased by ≥25%; or d. urine albumin-creatinine ratio ≥50 mg/mmol that has not decreased by ≥25% 3. Plasma creatinine >130 μmol/L and having risen to ≥115% but ≤130% of previous value	One of the following: 1. Mild/Stable proteinuria: a. urine dipstick ≥1+ but not fulfilling Category A & B criteria (only if other methods of urine protein estimation not available); or b. 24-hour urine protein >0.25 g but not fulfilling Category A & B criteria; or c. urine protein-creatinine ratio >25 mg/mmol but not fulfilling Category A & B criteria; or d. urine albumin-creatinine ratio >25 mg/mmol but not fulfilling Category A & B criteria 2. Rising blood pressure (providing the recorded values are >140/90 mm Hg) not fulfilling Category A & B criteria, defined as: a. systolic rise of ≥30 mmHg; and b. diastolic rise of ≥15mmHg	Previous involvement, currently inactive	No previous involvement

	BILAG Grade				
Organ System	A	В	С	D	E
	c. GFR <50 ml/min per 1.73 m², and last time was >50 ml/min per 1.73 m² or was not measured.				
	4. Active urinary sediment				
	5. Histological evidence of active nephritis within last 3 months				
	6. Nephrotic syndrome				
Haematological	TTP recorded as 2 (Same), 3 (Worse) or 4 (New) OR Any of the following: • Evidence of haemolysis and Haemoglobin <8 g/dl • Platelet count <25 x 10 ⁹ /l	TTP recorded as 1 (Improving) OR Any of the following: • Evidence of haemolysis and Haemoglobin 8-9.9 g/dl • Haemoglobin <8 g/dL (without haemolysis) • White cell count <1.0 x 10 ⁹ /L • Neutrophil count <0.5 x 10 ⁹ /L • Platelet count 25-49 x 10 ⁹ /L	Any of the following: • Evidence of haemolysis and Haemoglobin ≥10g/dl • Haemoglobin 8-10.9 g/dl • White cell count 1-3.9 x 10 ⁹ /L • Neutrophil count 0.5-1.9 x 10 ⁹ /L • Lymphocyte count <1.0 x 109/L • Platelet count 50-149 x 10 ⁹ /l • Isolated Coombs' test positive	Previous involvement, currently inactive	No previous involvement

Notes: BILAG=British Isles Lupus Assessment Group; GFR=Glomerular filtration rate.

